10.5. Covid-19 Related Protocol Deviations

Covid-19 related protocol deviations will be listed and summarised as per Section 9.9, using Table 4.1 and Table 4.2 from Section 9.10.4.

10.6. Tables to Present

10.6.1. Baseline Characteristics

Table 5. 1: Baseline characteristics, by treatment arm, for patients recruited to the trial before¹ the Covid-19 pandemic (CHRONOS-A)

See output of Table 1. 1, but for patients recruited to CHRONOS-A before the Covid-19 pandemic.

¹Patients were recruited before the Covid-19 pandemic if they were recruited to CHRONOS-A before 05/03/2020 (see Section 10.1)

Table 5. 2: Baseline characteristics, by treatment arm, for patients recruited to the trial during/after¹ the Covid-19 pandemic (CHRONOS-A)

See output of Table 1. 1, but for patients recruited to CHRONOS-A during/after the Covid-19 pandemic.

¹Patients were recruited during/after the Covid-19 pandemic if they were recruited to CHRONOS-A after 05/03/2020 (see Section 10.1)

Table 5. 3: Baseline characteristics, by treatment arm, for patients recruited to the trial before the Covid-19 pandemic (CHRONOS-B)

See output of Table 1. 5, but for patients recruited to CHRONOS-B before¹ the Covid-19 pandemic.

¹Patients were recruited before the Covid-19 pandemic if they were recruited to CHRONOS-B before 05/03/2020 (see Section 10.1)

Table 5. 4: Baseline characteristics, by treatment arm, for patients recruited to the trial during/after¹ the Covid-19 pandemic (CHRONOS-B)

See output of Table 1. 5, but for patients recruited to CHRONOS-B during/after¹ the Covid-19 pandemic.

¹Patients were recruited during/after the Covid-19 pandemic if they were recruited to CHRONOS-B after 05/03/2020 (see Section 10.1)

10.6.2. Analysis of End Points

Table 6. 1: Mean number of patients recruited and randomised per month per centre, for patients recruited to the trial before¹ the Covid-19 pandemic (CHRONOS-A and CHRONOS-B)

See output of Table 2. 2, but for patients recruited to the trial before the Covid-19 pandemic.

¹Patients were recruited before the Covid-19 pandemic if they were recruited to the trial before 05/03/2020 (see Section 10.1)

Table 6. 2: Mean number of patients recruited and randomised per month per centre, for patients recruited to the trial during/after¹ the Covid-19 pandemic (CHRONOS-A and CHRONOS-B)

See output of Table 2. 2, but for patients recruited to the trial during/after¹ the Covid-19 pandemic.

¹Patients were recruited during/after the Covid-19 pandemic if they were recruited to the trial after 05/03/2020 (see Section 10.1)

STATISTICAL ANALYSIS PLAN: FEASIBILITY

CHRONOS

Table 6. 3: Recruitment and randomisation rates¹, for patients recruited to the trial before² the Covid-19 pandemic (CHRONOS-A and CHRONOS-B)

See output for Table 2. 3, but for patients recruited to the trial before² the Covid-19 pandemic.

Table 6. 4: Recruitment and randomisation rates¹, for patients recruited to the trial during/after² the Covid-19 pandemic (CHRONOS-A and CHRONOS-B)

See output for Table 2. 3, but for patients recruited to the trial during/after² the Covid-19 pandemic.

Table 6. 5: Reasons for ineligibility, for patients recruited to the trial before¹ the Covid-19 pandemic (CHRONOS-A and CHRONOS-B)

See output for Table 2. 11, but for patients recruited to the trial before the Covid-19 pandemic.

¹Patients were recruited before the Covid-19 pandemic if they were recruited to the trial before 05/03/2020 (see Section 10.1)

Table 6. 6: Reasons for ineligibility, for patients recruited to the trial during/after¹ the Covid-19 pandemic (CHRONOS-A and CHRONOS-B)

See output for Table 2. 11, but for patients recruited to the trial during/after¹ the Covid-19 pandemic.

¹Patients were recruited during/after the Covid-19 pandemic if they were recruited to the trial after 05/03/2020 (see Section 10.1)

Table 6. 7: Reasons for withdrawal, for patients who withdrew from the trial before¹ the Covid-19 pandemic (CHRONOS-A and CHRONOS-B)

See output for Table 2. 12, but for patients who withdrew from the trial before the Covid-19 pandemic.

¹Patients were recruited before the Covid-19 pandemic if they were recruited to the trial before 05/03/2020 (see Section 10.1)

Table 6. 8: Reasons for withdrawal, for patients who withdrew from the trial during/after¹ the Covid-19 pandemic (CHRONOS-A and CHRONOS-B)

See output for Table 2. 12, but for patients who withdrew from the trial during/after¹ the Covid-19 pandemic.

¹Patients were recruited during/after the Covid-19 pandemic if they were recruited to the trial after 05/03/2020 (see Section 10.1)

¹Rate calculated out of total number of people approached

²Patients were recruited before the Covid-19 pandemic if they were recruited to the trial before 05/03/2020 (see Section 10.1)

¹Rate calculated out of total number of people approached

²Patients were recruited during/after the Covid-19 pandemic if they were recruited to the trial after 05/03/2020 (see Section 10.1)

STATISTICAL ANALYSIS PLAN: FEASIBILITY

CHRONOS

Table 6. 9: Summary statistics for time between consent and randomisation (Days), by treatment arm, for patients recruited to the trial before¹ the Covid-19 pandemic (CHRONOS-A)

Time between (Days)	Statistics	Focal	Radical	Total
Consent –	N	xxx	XXX	xxx
Randomisation	Mean (SD)	xx.xx (xx.xx)	xx.xx (xx.xx)	xx.xx (xx.xx)
	Median (IQR)	xx.xx (xx.xx to xx.xx)	xx.xx (xx.xx to xx.xx)	xx.xx (xx.xx to xx.xx)
	Missing – n (%)	xx (xx%)	xx (xx%)	xx (xx%)

¹Patients were recruited before the Covid-19 pandemic if they were recruited to CHRONOS-A before 05/03/2020 (see Section 10.1)

Table 6. 10: Summary statistics of time between consent and randomisation (Days), by treatment arm, for patients recruited to the trial during/after¹ the Covid-19 pandemic (CHRONOS-A)

See output for Table 6. 9, but for patients recruited to CHRONOS-A during/after¹ the Covid-19 pandemic.

Table 6. 11: Summary statistics for time between randomisation and treatment (Days), by treatment arm, for patients who underwent radical or focal treatment before the Covid-19 pandemic (CHRONOS-A)

Time between (Days)	Statistics	Focal	Radical	Total
Randomisation	N	XXX	XXX	XXX
- Treatment	Mean (SD)	xx.xx (xx.xx)	xx.xx (xx.xx)	xx.xx (xx.xx)
	Median (IQR)	xx.xx (xx.xx to xx.xx)	xx.xx (xx.xx to xx.xx)	xx.xx (xx.xx to xx.xx)
	Missing – n (%)	xx (xx%)	xx (xx%)	xx (xx%)

¹Patients who underwent treatment before the Covid-19 pandemic if they had a radical or focal treatment date before 05/03/2020 (see Section 10.1)

Table 6. 12: Summary statistics for time between randomisation and treatment (Days), by treatment arm, for patients who underwent radical or focal treatment during/after¹ the Covid-19 pandemic (CHRONOS-A)

See output for Table 6. 11, but for patients in CHRONOS-A who underwent radical or focal treatment during/after the Covid-19 pandemic.

Table 6. 13: Summary statistics of time between consent and randomisation (Days), by treatment arm, for patients recruited to the trial before¹ the Covid-19 pandemic (CHRONOS-B)

Time between (Days)	Statistics	Focal alone	Focal + finasteride	Focal + bicalutimide	Total
Consent –	N	XXX	XXX	XXX	XXX
Randomisation	Mean (SD) Median (IQR) Missing – n (%)	xx.xx (xx.xx) xx.xx (xx.xx to xx.xx) xx (xx%)			

¹Patients were recruited before the Covid-19 pandemic if they were recruited to CHRONOS-B before 05/03/2020 (see Section 10.1)

¹Patients were recruited during/after the Covid-19 pandemic if they were recruited to CHRONOS-A on/after 05/03/2020 (see Section 10.1)

¹Patients who underwent treatment during/after the Covid-19 pandemic if they had a radical or focal treatment date on/after 05/03/2020 (see Section 10.1)

STATISTICAL ANALYSIS PLAN: FEASIBILITY

CHRONOS

Table 6. 14: Summary statistics of time between consent and randomisation (Days), by treatment arm, for patients recruited to the trial during/after¹ the Covid-19 pandemic (CHRONOS-B)

See output for Table 6. 13, but for patients who were recruited to CHRONO-B during/after the Covid-19 pandemic.

¹Patients were recruited during/after the Covid-19 pandemic if they were recruited to CHRONOS-B on/after 05/03/2020 (see Section 10.1)

Table 6. 15: Summary statistics of time between randomisation and treatment (Days), between randomisation and neoadjuvant treatment (Days), and between start of neoadjuvant treatment and start of focal therapy (Days), by treatment arm, for patients who underwent focal treatment before the Covid-19 pandemic (CHRONOS-B)

Time between (Days)	Statistics	Focal alone	Focal + finasteride	Focal + bicalutimide	Total
Randomisation	N	XXX	XXX	XXX	XXX
Treatment	Mean (SD)	xx.xx (xx.xx)	xx.xx (xx.xx)	xx.xx (xx.xx)	xx.xx (xx.xx)
	Median (IQR)	xx.xx (xx.xx to	xx.xx (xx.xx to	xx.xx (xx.xx to	xx.xx (xx.xx to
	Missing – n	xx.xx)	xx.xx)	xx.xx)	xx.xx)
	(%)	xx (xx%)	xx (xx%)	xx (xx%)	xx (xx%)
Randomisation-	N	-	XXX	XXX	XXX
Neoadjuvant	Mean (SD)		xx.xx (xx.xx)	xx.xx (xx.xx)	xx.xx (xx.xx)
Drug Treatment	Median (IQR)		xx.xx (xx.xx to	xx.xx (xx.xx to	xx.xx (xx.xx to
	Missing – n		xx.xx)	xx.xx)	xx.xx)
	(%)		xx (xx%)	xx (xx%)	xx (xx%)
Start of	N	-	XXX	XXX	xxx
Neoadjuvant	Mean (SD)		xx.xx (xx.xx)	xx.xx (xx.xx)	xx.xx (xx.xx)
Drug Treatment	Median (IQR)		xx.xx (xx.xx to	xx.xx (xx.xx to	xx.xx (xx.xx to
- Focal	Missing – n		xx.xx)	xx.xx)	xx.xx)
Therapy	(%)		xx (xx%)	xx (xx%)	xx (xx%)

¹Patients who underwent treatment before the Covid-19 pandemic if they had a focal treatment date before 05/03/2020 (see Section 10.1)

Table 6. 16: Summary statistics of time between randomisation and treatment (Days), between randomisation and neoadjuvant treatment (Days), and between start of neoadjuvant treatment and start of focal therapy (Days), by treatment arm, for patients who underwent focal treatment during/after¹ the Covid-19 pandemic (CHRONOS-B)

See output for

Table 6. **15**, but for patients in CHRONOS-B who underwent focal treatment during/after the Covid-19 pandemic.

Table 6. 17: Summary statistics of time between consecutive visits (Days) from Screening Visit 1 to Visit 4², by treatment arm, for patients who underwent the most recent of the consecutive visits before¹ the Covid-19 pandemic (CHRONOS-A)

See output for Table 2. 6, but for patients in CHRONOS-A who underwent the most recent of the consecutive visits before¹ the Covid-19 pandemic.

¹Patients who underwent treatment during/after the Covid-19 pandemic if they had a focal treatment date on/after 05/03/2020 (see Section 10.1)

²Use treatment start date if blister pack return date unknown

¹Patients underwent the most recent of the consecutive visits before the Covid-19 pandemic if the date of visit of their most recent consecutive visit was before 05/03/2020 (see Section 10.1)

²Patients are expected to have reached Visit 3 by the end of the feasibility phase

STATISTICAL ANALYSIS PLAN: FEASIBILITY

CHRONOS

Table 6. 18: Summary statistics of time between consecutive visits (Days) from Screening Visit 1 to Visit 4², by treatment arm, for patients who underwent the most recent of the consecutive visits during/after¹ the Covid-19 pandemic (CHRONOS-A)

See output for Table 2. 6, but for patients in CHRONOS-A who underwent the most recent of the consecutive visits during/after¹ the Covid-19 pandemic.

¹Patients underwent the most recent of the consecutive visits during/after the Covid-19 pandemic if the date of visit of their most recent consecutive visit was on/after 05/03/2020 (see Section 10.1)

Table 6. 19: Summary statistics of time between consecutive visits (Days) from Screening Visit 1 to Visit 4², by treatment arm, for patients who underwent the most recent of the consecutive visits before¹ the Covid-19 pandemic (CHRONOS-B)

See output for Table 2. 7, but for patients in CHRONOS-B who underwent the most recent of the consecutive visits before¹ the Covid-19 pandemic.

¹Patients underwent the most recent of the consecutive visits before the Covid-19 pandemic if the date of visit of their most recent consecutive visit was before 05/03/2020 (see Section 10.1)

Table 6. 20: Summary statistics of time between consecutive visits (Days) from Screening Visit 1 to Visit 4², by treatment arm, for patients who underwent the most recent of the consecutive visits during/after¹ the Covid-19 pandemic (CHRONOS-B)

See output for Table 2. 7, but for patients in CHRONOS-B who underwent the most recent of the consecutive visits during/after¹ the Covid-19 pandemic.

¹Patients underwent the most recent of the consecutive visits during/after the Covid-19 pandemic if the date of visit of their most recent consecutive visit was after 05/03/2020 (see Section 10.1)

Table 6. 21: Proportions of patients, in each treatment arm, with a missing or delayed visit, for patients who underwent the visit before the Covid-19 pandemic (CHRONOS-A)

Visit ²		Focal	Radical	Total
Screening	Total	XXX	XXX	XXX
Visit 1	Delayed (n (%))	xxx (xx.x%)	xxx (xx.x%)	xxx (xx.x%)
	Missing (n (%))	xxx (xx.x%)	xxx (xx.x%)	xxx (xx.x%)
Visit 2	Total	xxx	xxx	XXX
	Delayed (n (%))	xxx (xx.x%)	xxx (xx.x%)	xxx (xx.x%)
	Missing (n (%))	xxx (xx.x%)	xxx (xx.x%)	xxx (xx.x%)
Visit 3	Total	xxx	xxx	XXX
	Delayed (n (%))	xxx (xx.x%)	xxx (xx.x%)	xxx (xx.x%)
	Missing (n (%))	xxx (xx.x%)	xxx (xx.x%)	xxx (xx.x%)

¹Patients underwent the visit before the Covid-19 pandemic if the date of visit was before 05/03/2020 (see Section 10.1)

²Patients are expected to have reached Visit 3 by the end of the feasibility phase

²Patients are expected to have reached Visit 3 by the end of the feasibility phase

²Patients are expected to have reached Visit 3 by the end of the feasibility phase

²Patients are expected to have reached Visit 3 by the end of the feasibility phase

STATISTICAL ANALYSIS PLAN: FEASIBILITY

CHRONOS

Table 6. 22: Proportions of patients, in each treatment arm, with a missing or delayed visit, for patients who underwent the visit during/after¹ the Covid-19 pandemic (CHRONOS-A)

See output for Table 6. 21, but for patients in CHRONOS-A who underwent the visit during/after¹ the Covid-19 pandemic.

Table 6. 23: Proportions of patients, in each treatment arm, with a missing or delayed visit, for patients who underwent the visit before¹ the Covid-19 pandemic (CHRONOS-B)

Visit ²		Focal + finasteride	Focal + bilutamide	Focal alone	Total
Screening Visit 1	Total	xxx	xxx	xxx	xxx
VISILI	Delayed (n(%))	xxx (xx.x%)	xxx (xx.x%)	xxx (xx.x%)	xxx (xx.x%)
	Missing (n(%))	xxx (xx.x%)	xxx (xx.x%)	xxx (xx.x%)	xxx (xx.x%)
Visit 2	Total	xxx	xxx	xxx	xxx
	Delayed (n(%))	xxx (xx.x%)	xxx (xx.x%)	xxx (xx.x%)	xxx (xx.x%)
	Missing (n(%))	xxx (xx.x%)	xxx (xx.x%)	xxx (xx.x%)	xxx (xx.x%)
Visit 3	Total	xxx	xxx	xxx	xxx
	Delayed (n(%))	xxx (xx.x%)	xxx (xx.x%)	xxx (xx.x%)	xxx (xx.x%)
	Missing (n(%))	xxx (xx.x%)	xxx (xx.x%)	xxx (xx.x%)	xxx (xx.x%)

¹Patients underwent the visit before the Covid-19 pandemic if the date of visit was before 05/03/2020 (see Section 10.1)

Table 6. 24: Proportions of patients, in each treatment arm, with a missing or delayed visit, for patients who underwent the visit during/after¹ the Covid-19 pandemic (CHRONOS-B)

See output for

Table 6. 23, but for patients in CHRONOS-B who underwent the visit during/after¹ the Covid-19 pandemic.

Table 6. 25: Treatment compliance (CHRONOS-A)¹, for patients who underwent radical or focal treatment before² the Covid-19 pandemic

See output for Table 2. 8, but for patients in CHRONOS-A who underwent radical or focal treatment before the Covid-19 pandemic.

Table 6. 26: Treatment compliance (CHRONOS-A)¹, for patients who underwent radical or focal treatment during/after² the Covid-19 pandemic

See output for Table 2. 8, but for patients in CHRONOS-A who underwent radical or focal treatment during/after² the Covid-19 pandemic.

¹Patients underwent the visit during/after the Covid-19 pandemic if the date of visit was on/after 05/03/2020 (see Section 10.1)

²Patients are expected to have reached Visit 3 by the end of the feasibility phase

²Patients are expected to have reached Visit 3 by the end of the feasibility phase

¹Patients underwent the visit during/after the Covid-19 pandemic if the date of visit was on/after 05/03/2020 (see Section 10.1)

²Patients are expected to have reached Visit 3 by the end of the feasibility phase

¹Data recorded at Visit 2

²Patients underwent treatment before the Covid-19 pandemic if their date of radical or focal treatment was before 05/03/2020 (see Section 10.1)

STATISTICAL ANALYSIS PLAN: FEASIBILITY

CHRONOS

Table 6. 27: Treatment compliance (CHRONOS-B)¹, for patients who underwent focal treatment before² the Covid-19 pandemic

See output for Table 2. 9, but for patients in CHRONOS-B who underwent focal treatment before² the Covid-19 pandemic.

Table 6. 28: Treatment compliance (CHRONOS-B)¹, for patients who underwent focal treatment during/after² the Covid-19 pandemic

See output for Table 2. 9, but for patients in CHRONOS-B who underwent focal treatment during/after² the Covid-19 pandemic.

Table 6. 29: Drug compliance (CHRONOS-B)¹, for patients who started neoadjuvant drug treatment before² the Covid-19 pandemic

See output for Table 2. 10, but for patients in CHRONOS-B who underwent neoadjuvant drug treatment before² the Covid-19 pandemic.

Table 6. 30: Drug compliance (CHRONOS-B)¹, for patients who started neoadjuvant drug treatment during/after² the Covid-19 pandemic

See output for Table 2. 10, but for patients in CHRONOS-B who underwent neoadjuvant drug treatment during/after² the Covid-19 pandemic.

¹Data recorded at Visit 2

²Patients underwent treatment before the Covid-19 pandemic if their date of radical or focal treatment was on/after 05/03/2020 (see Section 10.1)

¹Data recorded at Visit 2

²Patients underwent treatment before the Covid-19 pandemic if their date of focal treatment was before 05/03/2020 (see Section 10.1)

¹Data recorded at Visit 2

²Patients underwent treatment before the Covid-19 pandemic if their date of focal treatment was on/after 05/03/2020 (see Section 10.1)

¹Data recorded at Visit 2 and 3

²Patients underwent treatment before the Covid-19 pandemic if their date of neoadjuvant drug treatment was before 05/03/2020 (see Section 10.1)

¹Data recorded at Visit 2 and 3

²Patients underwent treatment before the Covid-19 pandemic if their date of neoadjuvant drug treatment was on/after 05/03/2020 (see Section 10.1)

STATISTICAL ANALYSIS PLAN: FEASIBILITY

CHRONOS

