6.7.3.2. CHRONOS-B¹

6.8. Randomisation

Randomisation will take place centrally via the InForm system. Randomisation will be blocked and stratified by the following stratification factors:

- Tumour grade (Gleason 6 [grade group 1], Gleason 7 [grade group 2], Gleason 7 [grade group 3])
- Local stage (T2 versus radiological (MRI) T3).
- CHRONOS-A only: Previous or current 5-alpha reductase inhibitor use.

7. Analysis Set

All objectives will be analysed using all patients approached for enrolment in the trial, and randomised patients according to the intention to treat principle.

8. Variables of Analysis

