9.5. Impact of the Covid-19 Pandemic

To assess the impact of the Covid-19 pandemic on the feasibility phase of the trial, we will assess the baseline demographics, recruitment rate, randomisation rate, reasons for ineligibility, and time between consent and randomisation to see if there exist important differences between the population recruited before the Covid-19 pandemic and the population recruited during/after the Covid-19 pandemic.

Time between randomisation and treatment, treatment compliance (CHRONOS-A and CHRONOS-B) and drug compliance (CHRONOS-B) will be assessed between the population who

Imperial Clinical
Trials Unit

STATISTICAL ANALYSIS PLAN: FEASIBILITY

CHRONOS

underwent treatment before the Covid-19 pandemic and those who underwent treatment during/after the Covid-19 pandemic.

Time between consecutive visits will be assessed between the population who underwent their most recent consecutive visit before the Covid-19 pandemic and those who underwent their most recent consecutive visit during/after the Covid-19 pandemic. Similarly, proportions of patients with missing or delayed visits will be assessed between patients who underwent that visit before the Covid-19 pandemic and those who underwent that visit during/after the Covid-19 pandemic.

Reasons for withdrawal will be assessed between the population who withdrew before the Covid-19 pandemic and the population who withdrew during/after the Covid-19 pandemic.

Trial processes and conduct will also be assessed for important differences between these populations. This analysis is detailed further in Section Error! Reference source not found.

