10.1. Analysis Populations

On 05/03/2020, Covid-19 was added to Public Health England's list of notifiable diseases in England and Wales (11).

Analysis Population	Population Definition	End Points
Patients randomised	Patients randomised to the trial	Baseline demographics
before the Covid-19 pandemic	before 05/03/2020	 Recruitment rate Reasons for ineligibility
 Patients randomised during/after the Covid-19 pandemic 	Patients randomised to the trial on/after 05/03/2020	Time between consent and randomisation
 Patients who underwent radical or focal treatment before the Covid-19 pandemic 	Patients whose radical or focal treatment start date is before 05/03/2020	 Time between randomisation and treatment Treatment compliance
Patients who underwent radical or focal treatment during/after the Covid-19 pandemic	Patients whose radical or focal treatment start date is on/after 05/03/2020	(CHRONOS-A and CHRONOS-B)
Patients who started neoadjuvant drug treatment before the Covid- 19 pandemic	 Patients whose neoadjuvant drug treatment start date is before 05/03/2020 (CHRONO- B only) 	Drug compliance (CHRONOS-B)
 Patients who started neoadjuvant drug treatment during/after the Covid-19 pandemic 	Patients whose neoadjuvant drug treatment start date is on/after 05/03/2020 (CHRONOS-B only)	
Patients who underwent their most recent consecutive visits before the Covid-19 pandemic	 Patients whose most recent date of visit is before 05/03/2020 	Time between consecutive visits
 Patients who underwent their most recent consecutive visits during/after the Covid-19 pandemic 	Patients whose most recent date of visit is on/after 05/03/2020	
 Patients who attended the visit in question before Covid-19 pandemic 	Patients whose date of visit is before 05/03/2020	 Proportions of patients with missing or delayed visits
 Patients who attended the visit in question after the Covid-19 pandemic 	Patients whose date of visit is on/after 05/03/2020	
 Patients who withdrew from the trial before the Covid- 19 pandemic 	Patients whose withdrawal date if before 05/03/2020	Reasons for withdrawal
 Patients who withdrew during/after the Covid-19 pandemic 	Patients whose withdrawal date is on/after 05/03/2020	

The following analyses will only be presented is there exist patients in both the before and during/after Covid-19 pandemic populations. Analyses for populations which do not contain any patients will be omitted as they are already included in the main analysis outlined in Section 9.

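### SAP Section 10 assigns men to a Covid-19 period by treatment date and visits by attendance, so never-treated men and missed visits enter neither period

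*SAP*

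**What the plan says.** Section 7 of the SAP states who is to be counted: "All objectives will be analysed using all patients approached for enrolment in the trial, and randomised patients according to the intention to treat principle".

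Section 10.1 then defines separate populations around 05/03/2020.

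- **Treatment compliance and time to treatment.** The earlier period is "Patients whose radical or focal treatment start date is before 05/03/2020"; the later period is the mirror image. Section 10.3 repeats this, and so do the table shells. For CHRONOS-A, the shell for the earlier period (Table 6.25) reads: "See output for Table 2. 8, but for patients in CHRONOS-A who underwent radical or focal treatment before the Covid-19 pandemic". The CHRONOS-B shell (Table 6.27) carries the same restriction: "but for patients in CHRONOS-B who underwent focal treatment before".
- **Missing or delayed visits.** The earlier population is "Patients who attended the visit in question before Covid-19 pandemic". Section 9.5 agrees: "proportions of patients with missing or delayed visits will be assessed between patients who underwent that visit before the Covid-19 pandemic". Section 10.4 defines a missed visit as one that yielded no information. Tables 6.21 to 6.24 have a Missing row and a Delayed row for Visits 1, 2 and 3.
- **Drug compliance in CHRONOS-B.** Section 10.1 and Tables 6.29 and 6.30 split by the date the drug was started.
- **Recruitment rate and ineligibility.** The later population is "Patients randomised to the trial on/after 05/03/2020". Tables 6.3 to 6.6 speak of recruited men, while Section 10.4 and the table footnote take the rate over all men approached.

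Section 10.4 also repeats the rule from Section 9.3: treatment compliance is viable if the lower 95% limit is at least 80%, needs remedial work between 70% and 80%, and goes to the TSC below 70%. The whole section is conditional: "The following analyses will only be presented is there exist patients in both the before and during/after Covid-19 pandemic populations".

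**The concern.** For treatment compliance, the condition for entering a period table is nearly the same as the condition for counting as compliant. A man whose treatment was cancelled has no treatment date, and a visit that did not happen has no visit date. Neither Section 9.5 nor Section 10 gives a substitute such as randomisation date or due date. The outcomes through which a pandemic would most plausibly show itself are the ones the tables leave out.

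The TSC could then read two compliance figures near 100% and two missed-visit counts of zero as evidence that nothing changed. The period denominators would add to the number of men treated, so they would not reconcile with Tables 2.8 and 2.9, which rest on all randomised men. The 80%/70% rule would be applied to figures that do not measure uptake.

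**Working it through.** **Who can enter each row**

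| Row | Needed to enter a period | Needed to count | Result |
|---|---|---|---|
| Treatment compliance, focal arms | treatment start date (10.1) | treatment date and completed details (5.1, 9.3, 10.4) | untreated men absent; only incomplete details, or a crossover under the allocated-treatment wording of 10.3, can lower it |
| Treatment compliance, radical arm | dated by the treatment visit (8.3, 10.4) | completed log details | untreated men with no date absent; crossovers, unfinished courses or a treatment visit without treatment can lower it |
| Missing visit | visit attended (9.5, 10.1) | no information collected (10.4) | 0/n in both periods |
| Delayed visit | visit attended | outside the visit window | estimable where a due date exists |
| Drug compliance | drug start date (10.1) | packs returned, or drug taken with no short-course deviation | men who never start are absent; the proportion can still vary |

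**Illustration 1** (assumed counts; every treated man has complete details and his allocated treatment). One 30-man CHRONOS-A focal arm:

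- randomised before 05/03/2020: 18 men, of whom 12 were treated before that date and 6 were waiting on it (3 treated later, 3 never treated);
- randomised on or after it: 12 men, of whom 9 were treated and 3 never treated.

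Under the SAP populations:

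- Table 6.25: 12/12 = 100%.
- Table 6.26: (3 + 9)/(3 + 9) = 12/12 = 100%.
- Denominators: 12 + 12 = 24, against 30 randomised.

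Table 2.8 would show 24/30 = 80.0%. The Wald lower limit is 0.80 − 1.96 × √(0.80 × 0.20/30) = 65.7%, and the exact lower limit is 61.4%. Both are below 70%.

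By randomisation date:

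- before: (12 + 3)/18 = 15/18 = 83.3%;
- on or after: 9/12 = 75.0%;
- check: 15 + 9 = 24 and 18 + 12 = 30, which reconciles with Table 2.8.

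**Illustration 2** (assumed). Fifteen men are randomised in each period, 14 and 10 of them are treated, and each is treated in the period in which he was randomised. The SAP tables show 14/14 and 10/10, both 100%. By randomisation date the figures are 14/15 = 93.3% and 10/15 = 66.7%, a fall of 26.7 percentage points that the SAP tables cannot show.

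**The 80%/70% rule on an n/n row.** The exact lower limit is 0.025^(1/n):

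- n = 10: 69.2%
- n = 12: 73.5%
- n = 16: 79.4%
- n = 17: 80.5%

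The grade therefore moves from TSC referral to viable on group size alone. With a Wald interval the lower limit is 100% at every n. The SAP names no interval method for compliance. The one interval it prints, in Section 11 for recruitment, reproduces as Wald: 0.33 ± 1.96 × √(0.33 × 0.67/60) = (0.211, 0.449).

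**Time to treatment.** Men treated before the cut-off are those whose waits were short enough to finish by then, so Tables 6.11 and 6.15 are right-truncated and understate the waiting time. In the drug arms, 05/03/2020 minus 84 days is 12/12/2019. A man randomised after that date who completes 84 days of drug cannot appear in the earlier rows of Table 6.15.

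**The case against.** The strongest reply is that this is a small descriptive section, shown only if both periods contain patients, with other sources nearby. Table 4.1 lists each deviation with its date. Table 4.2 has rows for missed study visits and for Covid-19-related deviations. Tables 6.7 and 6.8 give withdrawal reasons by period, and the CONSORT diagram gives attendance by visit. That stands in part: a reader could recover some counts. None of these outputs gives a period proportion over men randomised or visits due, which is what Section 9.5 says will be assessed.

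Several stronger readings are tempting, and the documents do not support them.

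- A reader might infer that the focal rows must equal exactly 100%. They need not. Entry requires a start date, whereas compliance also requires completed details, and Section 10.3 lets a crossover count against the arm. The supportable claim is bias towards 100%.
- A reader might infer that the rule will always return viable. That holds only with a Wald interval on an n/n row, and choosing Wald for compliance is an inference from Section 11.
- A reader might want a size for the truncation of time to treatment. It would depend on accrual before the cut-off and on waiting times, and the documents give neither. Only the direction is supported.
- A reader might infer that the decision to proceed is compromised. It is not, because Sections 9 and 11 do not use these period populations.

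It can also be said that recruited and randomised dates will usually coincide, since consent and randomisation share a visit. That is fair. What remains is that men approached but not randomised, including ineligible men, have no randomisation date by which to place them in a period.

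**Conclusion.** The Section 10 populations for treatment compliance and missed visits are wrong as written. Sections 9.5, 10.1 and 10.3 and the table shells all say the same thing, so this is not a slip in one table. Never-treated men and missed visits fall in neither period, contrary to Section 7. Treatment compliance by period is biased towards 100%, the Missing row is 0/n, and the 80%/70% rule does not measure uptake in these tables. Drug compliance shares the feature for men who never start the drug.

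The exclusion follows from the definitions and needs no assumption. Its numerical size does: the two illustrations use invented splits of a 30-man arm and show what can be hidden, not what will be. The finding is limited to the descriptive Covid-19 comparison.

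**What to change.** 1. **Treatment and drug compliance.** Classify by randomisation date (before, or on or after, 05/03/2020), with all men randomised to the relevant arm in that period as the denominator. Within the earlier group, keep everyone in the denominator and show a breakdown: treated before the date; withdrew untreated before the date; waiting on the date (treated later, or never treated). Do not report a proportion for the earlier group that leaves out the waiting men. In Illustration 1 that would again give 12/12. Group time to treatment by randomisation date too; Kaplan-Meier is optional.
2. **Visits.** Classify missed and delayed Visit 3 by its due date, 3 months after end of treatment with the ±4-week window, over all men due. Report never-treated men separately, because a visit timed from treatment has no due date for them. Drop or redefine the missed and delayed rows for Visits 1 and 2, which have no scheduled due date.
3. **Thresholds.** Do not apply the 80%/70% rule in Section 10.4 to tables restricted to treated men.
4. **Recruitment rate and ineligibility.** Use men approached, split by date of approach, or by month if individual dates are not held. A monthly split needs a stated rule for March 2020, which straddles the cut-off.

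The changes fall on Sections 9.5, 10.1, 10.3 and 10.4 and the shells for Tables 6.3 to 6.6, 6.11 to 6.12, 6.15 to 6.16 and 6.21 to 6.30. The cost is minor. Section 8.3 already lists randomisation, treatment, drug-start and visit dates, and monthly numbers approached by centre. Individual approach dates are not confirmed in the documents.
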